FRESENIUS MEDICAL CARE RENAL THERAPIES GROUP (RTG), LLC

TITLE:	A Randomized, Open Label, Cross-over Feasibility Study for Heparin-free Hemodialysis with the Dialyzer with Endexo [™] in End-Stage Renal Disease (ESRD)Subjects
PROTOCOL NUMBER:	Endexo-002
INVESTIGATIONAL PRODUCTS (IP):	Dialyzer with Endexo [™] , Fresenius Medical Care North America
SPONSOR:	Fresenius Medical Care RTG, LLC Medical Department, Clinical Research [name]

ORIGINAL PROTOCOL:

Version 1.0 [11AUG2020]

NCT04511338

PROTOCOL SYNOPSIS

	A Randomized, Open label, Cross-over Feasibility Study for Heparin-free	
Title	Hemodialysis with the Dialyzer with Endexo TM in End-Stage Renal Disease (ESRD)	
	Subjects	
Protocol Number	Endexo-002	
Study Type	Feasibility study	
Investigational Product (IP)	Dialyzer with Endexo, Fresenius Medical Care North America	
Proposed Indication	The dialyzer with Endexo used with either the CombiSet [®] bloodline ¹ or the Streamline [®] bloodline ² , and Citrasate [®] dialysate are intended for heparin-free hemodialysis treatments of patients with acute or chronic renal failure when conservative therapy is judged to be inadequate. The dialyzers with Endexo must be used in conjunction with dialysis machines equipped with ultrafiltration control and are to be used only as directed by a physician.	
	¹ Fresenius Medical Care North America ² B. Braun Medical Inc.	
Study Objective(s)The primary objective of this study is to explore the feasibility of heparin-free hemodialysis (HFHD) with two extracorporeal dialysis circuits (A, B) in ESRD subjects maintained on conventional hemodialysis (HD) with Citrasate dialysate regularly prescribed heparin.Study Objective(s)Circuit (A): dialyzer with Endexo and CombiSet bloodline Circuit (B): dialyzer with Endexo and Streamline bloodline		
	circuits.	
Study Design	 This is a randomized, open-label, cross-over study with subjects on thrice-weekly (incenter) hemodialysis. The study consists of a Screening Period, two Study Periods (1 and 2), a Washout Period and a Follow-up Visit. A study design diagram is presented in Appendix I. After screening, chronic kidney disease subjects on thrice weekly conventional HD with Optiflux dialyzer (F160NR and F180NR), standard of care (SOC) bloodline, Citrasate dialysate, and regularly prescribed heparin dose will be assigned randomly to one of the treatment sequences: AB or BA. Circuit (A) includes the dialyzer with Endexo and the CombiSet bloodline. Circuit (B) includes dialyzer with Endexo and the Streamline bloodline Each sequence includes two study periods (Period 1 and Period 2) and a Washout period. 	
	• Period 1 and Period 2 consist of 5 HD sessions per period (5 Visits per period): The 1st HD session with the regularly prescribed Heparin dose, the 2nd HD	

	session with 50% of the prescribed Heparin dose, and the 3rd, 4th and 5th HD sessions with 0% Heparin (heparin-free).					
	• The Washout period is performed between Period 1 and Period 2. It consists of 3 conventional HD sessions (3 Visits).				sts of	
	The tables below provide a summary for study periods and HD visits:Table 1:Summary of Study Periods					
	Randomization	(F 1	Period 1 ive Visits: .,2,3,4,5)	Washout Period***	Period 2 (Five Visits: 9,10,11,12,13)	
	Sequence AB		A*	(Three Visits: 678)	B**	
	Sequence BA		B**	0,7,0)	A*	
	*Circuit A: dialyzer with Endexo + CombiSet bloodline **Circuit B: dialyzer with Endexo + Streamline bloodline ***Conventional HD					
	Table 2:Summary of HD Visits during Periods 1 and 2					
			Period 1 ar (Circuit	nd Period 2 A or B)		
	Visit 1 and Visit 9		Regularly pre	scribed Heparin dose	2	
	Visit 2 and Visit 1050% of the regularly prescribed Heparin dose					
	Visit 3 and Visit 11	-	0% Heparin (Heparin-free)		
	Visit 4 and Visit 12	4 and Visit 12 0% Heparin (Heparin-free)				
	Visit 5 and Visit 13	3	0% Heparin (Heparin-free)			
	Table 3: Summary of the Washout Period					
			Washou	t Period		
	Visits 6, 7, and 8		Conventional	HD		
Study Population	The study population will consist of ESRD subjects who are a minimum of 22 years of age and have been prescribed in center thrice weekly HD for at least 180 days prior to the date of signed informed consent.			ars of rior to		
Total Number of Subjects	12–16 eligible subjec	cts will	l be enrolled			
Total Number of Sites	1–2 (United States)					

	Each subject will participate in the study for approximately 10 weeks.
Estimated Duration of Study	• Screening Period up to 4 weeks
	 Two Study Periods (Period 1 and Period 2) including 5 HD sessions per period (approximately 2 weeks per subject per period).
	 A Washout Period includes 3 HD sessions (1 week) between the Study Periods 1 and 2.
	• A Follow-up Visit within one week of the subject's last study HD session.
	After the subject's last study HD session, the subject will resume HD as prescribed by his/her physician.
	A subject who signed the ICF must meet all the following inclusion criteria in order to be eligible for enrollment in the study:
	 Must be an adult, defined as having had a 22nd birthday on or before the date of signed informed consent
	2. Has been prescribed in center thrice weekly HD for at least 180 days prior to the date of signed informed consent
	 Has been on Conventional HD for at least 30 days prior to the date of signed informed consent. Conventional HD includes: Optiflux dialyzer (F160NR or F180NR), SOC bloodline, Citrasate dialysate, and regularly prescribed heparin dose.
	 Has a prescribed HD treatment duration ≥180 minutes (3 hours) and ≤270 minutes (4.5 hours) at the time of signed informed consent
Inclusion Criteria	5. Has a well-established functional permanent vascular access (AVF, AVG) that can allow a blood flow of at least 250 mL/min
	 Has been on a regularly prescribed heparin dose for HD and has had no change in heparin prescription within 14 days prior to the date of signed informed consent
	7. Has the following most recently available laboratory results within 45 days prior to the date of signed informed consent:
	a. Single pool Kt/V (spKt/V) ≥ 1.2
	b. Hemoglobin $\geq 9 \text{ g/dL}$
	c. Platelet count $\geq 100,000/\text{mm}^3$
	8. A female of childbearing potential must have a negative serum pregnancy test at the time of screening and agree to use an acceptable method of contraception during the study
	A subject who signed the ICF is excluded from the study if any of the following criteria are met:
	1. Known allergic reactions to Endexo
Exclusion Criteria	2. Known heparin contraindications
	3. Hospitalization within 30 days prior to the date of signed informed consent
	4. Presence of active malignancy, congestive heart failure New York Heart Association (NYHA) Class III or IV (see Appendix III), or liver cirrhosis

	 Is receiving or has received chemotherapy/radiation therapy/immunotherapy/plasmapheresis therapy within 90 days prior to the date of signed informed consent
	6. Is receiving oral or/and intravenous (IV) antibiotics or has used oral or/and IV antibiotics within 14 days prior to the date of signed informed consent
	7. Is currently enrolled in or has completed any other investigational product study within 30 days prior to the date of signed informed consent
	8. Is receiving anticoagulants including vitamin K antagonists
	9. Is receiving a glycoprotein platelet inhibitor
	10. Is receiving more than one anti-platelet medication
	11. Is receiving systemic heparin therapy for prevention or treatment besides heparin prescribed for dialysis
	12. Requiring blood and other labile blood products (for e.g., fresh frozen plasma, platelets) transfusion during HD treatments
	13. Has history of clotting or bleeding disorders
	14. Has history or current evidence of any condition, therapy, or laboratory abnormality that might interfere with the participant's ability to follow the requirements of the study and participate for the full duration of the study, or is not in the best interest of the subjects to participate, in the opinion of the investigator.
	Primary endpoint:
	• The number and percent (%) of successful heparin-free HD* sessions for each subject in each circuit
	*Definition of a successful HD Session:
	A successful HD session must meet all the following criteria:
	1. Absence of complete HD circuit occlusion (Grade 4) rendering dialysis impossible
	2. Absence of the need to replace dialyzers or bloodlines due to clotting
Study Endnoints	3. Absence of saline flushes to maintain blood flow through the circuit during the HD session
Study Enupoints	4. Absence of any additional heparin beyond what is allowed per study visits
	5. Single pool Kt/V (spKt/V) \geq 1.2
	Secondary endpoint:
	• Adverse events and device-related adverse events
	Additional Assessments:
	• Number and percentage of dialyzers and bloodlines for each clotting grade using the visual inspection clotting grade scale (Appendix II)
	• HD treatment duration or time to complete circuit occlusion (Grade 4)
	Blood volume processed per dialysis session

	• The volume, the time of saline administered and the reason for administration per subject per HD session (other than for circuit priming or rinse back)				
	• Urea Reduction Ratio (URR) and spKt/V for all HD sessions				
Exploratory Assessment	Pictures of the arterial and venous end caps of the dialyzer with Endexo, arterial and venous drip chambers for CombiSet bloodline and venous chambers, arterial and venous pods for Streamline bloodline will be taken by the study sites at the end of each HD session.				
	The data listed below will be collected in the study:				
	1. Demographics				
	2. Medical History, historical laboratory values and Concomitant Medications				
	3. Physical Exam, Vital Signs, Body Measurements (height, weight)				
	4. Adverse events, serious adverse events, and device deficiencies				
	5. HD Treatment parameters:				
	a. Initial HD Prescription				
	b. Data collection during dialysis treatment:				
	 Blood flow rate (Qb), dialysate flow rate (Qd), arterial pressure (AP), venous pressure (VP), at initiation of the HD sessions and every 30±15 minutes 				
	 KECN recorded at initiation of the HD sessions and every 30±15 minutes 				
	c. HD Treatment Data:				
	 Treatment Time (Td), mean Qb, mean Qd, mean AP and VP, mean ultrafiltration volume and rate, and blood volume processed 				
Data Collection	 Mean KECN 				
	d. Volume, time and the reason for saline flushes administration (other than for circuit priming or rinse back)				
	e. HD Treatment-related Medications (total heparin units given [bolus + maintenance]) when applicable				
	f. Duration of blood flow cessation during hemodialysis treatment estimated as the difference between the Ultrafiltration (UF) clock and the Remaining Time on Dialysis (RTD) clock.				
	6. Thrombus scoring at the end of each HD session:				
	a. Visual thrombus scoring of dialyzer end caps, and bloodline drip chambers and pods will be performed (Grade 1–4) and recorded by site staff (the investigator or a designee). For further details, see Appendix II.				
	b. Digital pictures of the dialyzer end caps, and bloodline drip chambers and pods will be taken by site staff.				
	7. Laboratory Assessments:				
	a. At screening:				
	 Serum pregnancy test for females of childbearing potential 				

	b. Periods 1 and 2:
	 Pre- and post-hemodialysis for Visits (1–5) and (9–13):
	 Complete Blood Count with differential (CBC with diff), Blood Urea Nitrogen (BUN), and Albumin
	 Pre- and post-hemodialysis for Visits 1,3, 9 and 11:
	 β₂ Microglobulin (B2M), C-Reactive Protein (CRP), Interleukin-6 (IL-6) and Ferritin
Sample Size Determination	For this feasibility study, we proposed to enroll 12–16 eligible subjects. The sample size was not calculated based on any estimates or comparisons.
	Analysis for primary endpoint:
	The descriptive statistics (n, mean, standard deviation, median, minimum, and maximum) will be presented for the number and percent of successful heparin-free HD sessions for each circuit. The frequency for subjects with possible successful heparin-free sessions (0, 1, 2, or 3) will be displayed for each circuit.
	Analysis for secondary endpoints:
Statistical Methods	The number and percent of subjects with adverse events, and the number of adverse events will be presented for each circuit by system organ class and preferred term using MedDRA. The device-related adverse events will be listed for each circuit.
	Additional assessments.
	Descriptive statistics (n, mean, standard deviation, median, minimum and maximum) will be presented for continuous endpoints for each circuit. Frequency and percent will be presented for categorical endpoints for each circuit.
	All adverse events (AE) and serious adverse events (SAE) regardless of relatedness to the Investigational Product (IP) will be captured from the time the subject signs the ICF until the subject completes or withdraws from the study.
S a fater	The site investigator must inform the Sponsor of every SAE, within 24 hours of
Safety Monitoring/Safety Oversight	The study medical monitor will evaluate and monitor safety of the subjects during the study.
	If the Sponsor determines that an unanticipated adverse event or serious adverse event presents an unreasonable risk to the subjects, the Sponsor will terminate the study as soon as possible.

APPENDIX I: Study Design Endexo-002

Appendix II: Clotting scales

During Period 1 and 2, an investigator or designee is to perform thrombus scoring on dialyzer arterial and venous end caps, and bloodline drip chambers and pods at the end of dialyzer/bloodline use. All observers will be trained on the scoring prior to study start. The same observer should perform the evaluations as much as possible throughout the study. After use, the observer is to select one of the 4 possible grades as described in the tables below (The pictures in the tables are for reference only. The observer must assign the grade based on the description, not the pictures).

The following areas of the circuits need to be scored:

Dialyzer with Endexo: 1) arterial end cap and 2) venous end cap

CombiSet bloodline: 1) arterial chamber and 2) venous chamber

Streamline bloodline: 1) venous Chamber, 2) arterial pod and 3) venous pod

a) Dialyzer arterial and venous end caps

Thrombus scoring is to be performed at the end of dialyzer use for every dialyzer used in the study. Visual inspections of the dialyzer arterial and venous end caps will be done after the rinseback process has been completed by the clinical staff. This graded scoring method has been adopted from Dorsch et al.² and Laville et al.³

Grade 1	Grade 2	Grade 3	Grade 4
Good, clear dialyzer; no detectable clotting	Overall light redness; minimal clot formation	Overall moderate redness; clot formation but nonobstructive and dialysis still possible	Complete occlusion of the dialyzer rendering dialysis impossible

Bloodline	Grade 1	Grade 2	Grade 3	Grade 4
Description	Clean dialysis blood line and bubble trap	Fibrin ring in the bubble trap or blood line	Nonobstructive clot in the blood line or bubble trap	Complete clotting and occlusion of the HD circuit rendering dialysis impossible
Examples of Chambers				
Examples of Pods			O,	

b) Bloodline Drip Chambers and Pods

This graded scoring method has been adopted from Islam et al.

increases.

1. STUDY OBJECTIVES

1.1. Primary Objective

The primary objective of the study is to explore the feasibility of heparin-free hemodialysis (HFHD) with two extracorporeal dialysis circuits (A) and (B) in ESRD subjects who are maintained on conventional hemodialysis (HD) with Citrasate dialysate and regularly prescribed heparin. Circuit (A) includes the dialyzer with Endexo and Combiset bloodline; and Circuit (B) includes the dialyzer with Endexo and Streamline bloodline.

1.2. Secondary Objective

The secondary objective is to collect and summarize adverse events with both dialysis circuits.

2. STUDY DESIGN

2.1. General Description

This is a randomized, open-label, cross-over study with subjects on thrice-weekly (in-center) hemodialysis. The study consists of a Screening Period, study Period 1, Washout Period, study Period 2, and a Follow-up Visit.

• Screening Period:

The Screening Period begins with signing of the informed consent form (ICF) and can extend up to 4 weeks in duration. After completing all required tests/procedures and determining/verifying the eligibility, the subject is randomly assigned to one of the circuit sequences, either AB or BA. The randomization is done in the electronic data capture (EDC) system.

Circuit A consists of the dialyzer with Endexo and CombiSet bloodline and Circuit B consists of the dialyzer with Endexo and Streamline bloodline.

• Period 1:

Period 1 consists of 5 HD sessions (Visits 1 to 5) on the dialyzer with Endexo with the CombiSet bloodline for sequence AB and Streamline bloodline for sequence BA according to the randomization, and different heparin doses shown below:

Visit 1: 100% of heparin as prescribed

Visit 2: 50% of heparin as prescribed

Visits 3, 4, 5: 0% of heparin

This period lasts for approximately two weeks per subject.

Version 2.0 6/30/2021 Page 3 of 13

Washout Period:

The Washout Period occurs between Period 1 and Period 2. It consists of three conventional HD sessions (Visits 6, 7, and 8). This period lasts approximately one week per subject.

• Period 2:

Period 2 consists of 5 HD sessions (Visits 9 to 13) on the dialyzer with Endexo with Streamline bloodline for sequence AB and CombiSet bloodline for sequence BA according to the randomization, and different heparin doses shown below:

Visit 9: 100% of heparin as prescribed,

Visit 10: 50% of heparin as prescribed,

Visits 11, 12, 13: 0% of heparin

• Follow-up Visit:

An in-center Follow-up Visit is to be conducted within 1 week of the subject's last scheduled study HD treatment. This visit cannot be combined with the last study HD visit.

2.2. Method of Assigning Subjects to Treatment Groups

Eligible subjects will be randomly assigned to one of the 2 sequences AB or BA as follows:

	Period 1	Period 2
Sequence AB	Circuit (A)	Circuit (B)
Sequence BA	Circuit (B)	Circuit (A)

The study planned to recruit subjects at two sites. To keep the balance, a randomization block of 2 was used. The randomization chart was generated in 10 randomization blocks, a total of 20 subjects for each site. The chart was loaded to Medidata RAVE Randomization and Trial Supply Management (RTSM).

2.3. Blinding

N/A

2.4. Determination of Sample Size

Version 2.0 6/30/2021 Page 4 of 13

A sample size was not calculated. A total of 12 to 16 subjects with three heparin free HD treatments for each circuit for each subject or 36 to 48 HD sessions per circuit was considered appropriate for a feasibility study.

3. CHANGES IN THE CONDUCT OF THE STUDY OR PLANNED ANALYSES

3.1. Changes in the Conduct of the Study

Concurring with FDA's comments/suggestions, the withdrawal criteria when clotting score (CS) = 4 in a HD treatment are as follows:

- If CS=4 in dialyzer, the subject will be withdrawn from the study
- If CS=4 in circuit A bloodline (CombiSet), Period 1, the subject will proceed to washout
- If CS=4 in circuit A bloodline (CombiSet), Period 2, the subject will be withdrawn from the study, and
- If CS=4 in circuit B bloodline (Streamline) in any period, the subject will be withdrawn from the study.

3.2. Changes in the Planned Analyses

Concurring with FDA's comments/suggestions, the secondary endpoint of adverse events, and device-related adverse events, became the primary safety endpoint.

4. EFFICACY AND SAFETY ENDPOINTS

4.1 Primary Endpoint

The primary endpoint is the number and percent (%) of successful heparin-free HD sessions for each subject in each circuit. A successful HD session must meet all the following criteria:

- 1. Absence of complete HD circuit occlusion (Grade 4) rendering dialysis impossible
- 2. Absence of the need to replace dialyzers or bloodlines due to clotting
- 3. Absence of saline flushes to maintain blood flow through the circuit during the HD session
- 4. Absence of any additional heparin beyond what is allowed per study visits
- 5. Single pool Kt/V (spKt/V) \geq 1.2

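### The success definition has no criterion for delivered against prescribed time, so a heparin-free session ended early for clotting short of Grade 4 can be counted as successful

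*SAP*

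**What the plan says.** SAP 4.1 and the Study Endpoints row of the Protocol Synopsis give the same closed list of five criteria, all of which are required. In order, they are:

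1. On occlusion, the wording is "Absence of complete HD circuit occlusion (Grade 4) rendering dialysis impossible".
2. On replacement, the test is one of need and not of the act itself: "Absence of the need to replace dialyzers or bloodlines due to clotting".
3. Saline must not have been used to keep blood moving in the circuit.
4. Heparin must not exceed the amount permitted at that visit.
5. The session must reach an spKt/V of 1.2 or more.

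Protocol Appendix II defines the grades. Dialyzer Grade 3 is "Overall moderate redness; clot formation but nonobstructive and dialysis still possible"; Grade 4 is complete occlusion that makes dialysis impossible. Eligible subjects have a prescribed session of 180 to 270 minutes and a recent spKt/V of at least 1.2, with no upper limit (Synopsis, Inclusion Criteria).

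Treatment duration is an additional assessment (SAP 4.3), summarised by circuit and heparin level (SAP 6.8). The Synopsis (Data Collection) lists the initial prescription, treatment time and a reason for each saline flush. It lists no reason for ending a session early.

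**The concern.** The study asks whether a dialysis session can be run without heparin. When a circuit is clotting, staff could flush it, replace part of it, add heparin, or return the blood and stop. The first three are named as failures; the fourth is not. If staff stop before the circuit occludes, the only criterion left that responds to lost time is the spKt/V floor. That floor is fixed, equals the entry floor and is not tied to the subject's own prescription.

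At stake is the count that forms the primary result. A session that clotting cut short could enter it as evidence of feasibility. No session is wrongly counted as a failure by this route, so the error runs one way. Because the study is open-label, whoever classifies such a session knows the circuit and the heparin dose.

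**Working it through.** **Step 1. The plan's own figure.** SAP 2.4 gives 36 to 48 heparin-free sessions per circuit: 12 × 3 = 36 and 16 × 3 = 48. It reproduces.

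**Step 2. Run the case through the criteria.** Take a session stopped for clotting while blood still flows, with no flush, replacement or added heparin.
- Criterion 1: met if the rater does not assign Grade 4.
- Criterion 2: nothing was replaced. Whether replacement was needed is open to judgement.
- Criteria 3 and 4: met.
- Criterion 5: depends on how much time was lost.

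**Step 3. How much time can be lost before criterion 5 fails?** The documents give only the 1.2 floor, so full-session values of 1.3 to 1.8 are assumptions. Both models below assume clearance stays undiminished until the stop.

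*Simple model.* If spKt/V is proportional to delivered time, the tolerable loss is a fraction 1 − 1.2/k of the session, where k is the full-session spKt/V. For k = 1.3 this is 1 − 1.2/1.3 = 7.7%; for 1.6 it is 25.0%; for 1.8 it is 33.3%; for 1.2 it is zero.

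*Second-generation logarithmic formula.* SAP section 7 cites a paper on this method but the SAP does not print the formula, so its usual form is taken as an assumption:

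spKt/V = −ln(R − 0.008t) + (4 − 3.5R) × UF/W

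R is the post/pre urea ratio, t is hours, and UF/W is ultrafiltration over body weight, set at 3% for the full session (assumed). Urea is taken to fall log-linearly, and ultrafiltration in proportion to time.

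Example, 240 minutes and k = 1.6:
- At t = 4, R = 0.2537 gives −ln(0.2537 − 0.032) + (4 − 0.888) × 0.03 = 1.507 + 0.093 = 1.60.
- After a fraction 0.7735 of the session, t = 3.094, R = 0.2537^0.7735 = 0.346 and UF/W = 0.0232. Then −ln(0.346 − 0.0248) + (4 − 1.211) × 0.0232 = 1.135 + 0.065 = 1.20.
- Time delivered is 0.7735 × 240 = 186 minutes, so 54 minutes (23%) can be lost.

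Minutes that can be lost with spKt/V still at 1.2 (share of session):

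| Full-session spKt/V | 180 min | 240 min | 270 min |
|---|---|---|---|
| 1.2 | 0 | 0 | 0 |
| 1.3 | 13 (7%) | 17 (7%) | 18 (7%) |
| 1.4 | 24 (13%) | 31 (13%) | 34 (13%) |
| 1.5 | 33 (18%) | 43 (18%) | 48 (18%) |
| 1.6 | 42 (23%) | 54 (23%) | 61 (22%) |
| 1.8 | 56 (31%) | 73 (30%) | 81 (30%) |

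Varying UF/W from 0 to 4% changes these by less than 1 minute. The share depends on the subject's spKt/V and hardly on the length of the prescription.

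**Step 4. Effect on the endpoint.** One reclassified session moves that subject's circuit percent by 1/3 = 33.3 points. It moves the pooled circuit rate by 1/36 = 2.8 points or 1/48 = 2.1 points; three sessions move it by 8.3 or 6.2 points.

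**Step 5. Would the planned tables show it?** SAP 5.1 and 5.2 average the 0% heparin sessions within each subject before summarising. A single 54-minute loss then appears as 54/3 = 18 minutes in that subject's mean. No planned summary sets delivered against prescribed time.

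**The case against.** The strongest objection is that criterion 2 tests need, not the act of replacing. If clotting ends a session with time remaining, finishing it would plausibly have required new components, so the session may already fail. This stands in part. A reader might infer that every such session is scored a success, and the text does not support that. Nor does it say that such a session fails; the outcome is left to an unblinded reading.

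A reader might also infer that a partly obstructing clot is by definition below Grade 4. Appendix II does not settle it. Grade 3 is non-obstructive with dialysis still possible, Grade 4 is complete occlusion, and a clot between the two fits neither. The rater must choose.

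The minutes are upper bounds. Progressive clotting may well lower clearance before the stop, which makes criterion 5 more likely to fail. It is also tempting to say the problem is worst with long prescriptions; that is true in minutes but not as a share of the session.

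The documents do not describe staff stopping early for clotting, so frequency is unknown. One might add that SAP 3.1, which sets different withdrawal rules for Grade 4 in the two bloodlines, encourages early stopping unequally by circuit. That is conjecture, and no bias in the A-versus-B comparison is shown.

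Finally, the study is descriptive with no success threshold, and SAP 5.1 lists all data, so a reader could look for short sessions afterwards. This limits the harm, but it does not correct the primary table.

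**Conclusion.** The concern holds as a gap in the endpoint rule. The five criteria do not refer to delivered time, and the rule as written can count a session ended early for clotting as a success. The open reading of criterion 2 may catch some of these sessions, and the spKt/V floor catches those in subjects with little reserve. The remaining error can only raise the success rate.

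The size of the gap is at most about 7% to 31% of prescribed time for assumed full-session spKt/V of 1.3 to 1.8, given undiminished clearance. The effect on the reported rate depends on how many such sessions occur, which the documents do not allow anyone to estimate. The point deserves correction because it affects the primary count and the correction is cheap. It does not show that the result is wrong.

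**What to change.** 1. State in SAP 4.1, with matching text in the protocol, that a session ended before the prescribed time because of clotting is not successful, and that criterion 2 is read that way. Use any reason for early end found in the source or listed data.
2. Report delivered against prescribed time for each heparin-free session, by circuit. Treatment time and the initial prescription are already collected, and SAP 6.3 already lists prescription changes.
3. Repeat the primary table as a sensitivity analysis, counting as not successful any session short of prescription by more than a pre-stated margin, for example 15 minutes. Show sessions known to be shortened for other reasons separately.

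The margin is a convention that the sponsor may set differently. The change classifies an endpoint and alters no treatment rule.

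Cost: a sentence in the endpoint definition and two tables. SAP 5.7 describes enrolment in the past tense, so a new case report form field may come too late; items 2 and 3 need none. The success rate may look slightly less favourable. Where the reason for a short session is unknown, the sensitivity table may count some sessions shortened for other reasons as failures, so it should supplement the primary table and not replace it.
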